4.3 Safeguards against coercion and bias during the recruitment and consenting

4.3.1 Sub-study 1: To ensure there is ample time for the participant to consider participating, they will be provided with the informed consent form through DocuSign which includes a detailed summary of the study at the time the study team reaches out to the potential participant to report positive test findings, and gauge general interest in the study. When the participant comes to the EM tent for screening labs, an appropriately delegated and credentialed clinical investigator from the EM Department will review the consent form with the individual and address any questions.

4.3.2 Sub-study 3: Recruitment will occur through a survey, or in person information sessions. This initial introduction to the study will not be made by any employee's direct supervisor or a person in the supervisory hierarchy. This is intended to minimize any feelings of undue influence in recruiting amongst the UPHS healthcare workforce allowing for autonomy in decisions to participate.

Safeguards against coercion: UPHS employees who are under the direct supervision of the study PI and/or sub-Investigators are at an increased risk for undue coercion to participate and considered to be a vulnerable population. Assuming that Emergency Medicine and Infectious Disease study team physicians and study team nurses will enroll into Sub-study 3 as participants, a physician investigator from the alternate department will consent the UPHS worker onto this sub-study. For example, if a study physician in EM wants to enroll, the physician investigator obtaining consent would then be from ID. The delegated physician investigator that consents the participant in this sub-study will remind the participant that the decision about research participation will not affect (favorably or unfavorably) performance evaluations, career advancement, or other employment-related decisions made by peers or supervisors. Documentation of these conversations will be recorded as part of the informed consent process and provided in the informed consent document. EM and ID division leadership will be educated for awareness that they may not utilize enrollment in making any decisions about staff performance or advancement. These measures are put into place to minimize any undue coercion and allow for autonomy in decisions to participate. The PI, Primary ID Sub-Investigator Contact and/or Primary EM Sub-Investigator Contact will not enroll to participate personally as participants in the research, this will ensure that there is always at least one non-participating clinical investigator for study operations and ensure the integrity of the data analysis remains intact (unbiased).

Safeguards against bias for physicians with dual roles: Any PATCH trial sub-investigator physician (or study team member) who is enrolled as a participant into Sub-study #3 will be removed from certain elements of the study conduct to minimize bias. Such a person with a dual role as both a trial participant and trial study team member:

- a. would not be able to perform data entry, review, evaluations associated with their own data; data should be entered, reviewed, and evaluated by a member from the alternate division
- b. would not be able to perform data analysis, if the analysis is identifiable; aggregate analysis could be partially allowable in certain circumstances
- c. would have some restrictions in performing informed consent for patients enrolling into Sub-study #1 —as above, the physician investigator would not be allowed to mention to the prospective patient being consented that the physician was also participating in the study--- minimizing bias of safety and therapeutic benefit ("if my

doctor enrolled, then it's safe and so should I').

4.4 Consenting process

4.4.1 Sub-study 1 and 3: Informed consent will be performed via DocuSign, an electronic mechanism that is both HIPAA and 21 CFR Part 11 compliant. It is important for infection control and research staff safety to use e-consent approaches; use of paper with wet signatures represents an excessive risk of contaminated fomites.

Appropriately delegated and credentialed physician investigators will conduct the consent process and answer any questions from participants via telephone. The e-consent will be obtained via the participant's smartphone/smart device.

4.4.2 Sub-study 3: For this sub-study 3, consent forms will include additional details relevant to healthcare workers as a vulnerable population, ensuring (a) that any medical data collected will not be shared with Penn managers or affect employment, (b) that agreement or refusal to participate will not impact employment or be included in any personnel files, and that (c) physician sub-investigators obtaining consent are not direct supervisors of any participants undergoing enrollment.

4.3 Required Registration information

- Patient's initials (first and last)
- Patient's Hospital ID and/or last 4 digits of Social Security number
- Patient past medical history
- Body mass Index
- Smoking status Current former
- Gender
- Birth date (mm/yyyy)
- Race
- Ethnicity
- Nine-digit ZIP code
- State of residence
- County of residence
- Cell phone number and alternate numbers
- Email address
- Sub-study 1: A description (not containing PHI) for all full time inhabitants at the residence where the participant will stay during the 14-day quarantine.

5.0 RANDOMIZATION

After all applicable screening assessments have been performed, participants who have met all inclusion criteria and none of the exclusion criteria will be centrally, randomly allocated to one of the two groups in each sub-study. Randomization will be done using computer generated randomization numbers. Treatment **should start within 3 working days after randomization.** Once the order for study drug arrives at the

The PATCH Trial

pharmacy and the participant is randomized only the pharmacist is aware of the assignment of HCQ versus placebo in the double blind sub-studies (1 and 3).

Blinding: Sub-Study 1 and 3 will have a double-blind placebo controlled design.

Unblinding: Sub-Study1: If a participant progresses with symptoms of COVID-19 based on the assessment scale outlined below an appropriately delegated and credentialed study team member will review the case with a clinical investigator who will sign off on the need to un-blind the participant. If the participant was on placebo and continues to have symptoms, then he/she will be allowed to crossover to the HCQ dosing. The EM van will deliver the HCQ to the participant. If the patient was on HCQ then HCQ will be stopped and the patient will be asked to seek the advice of their primary care doctor or go to the emergency room if symptoms are becoming more worrisome. Participants who have progressive symptoms and are subsequently hospitalized due to COVID-19 will be unblinded but not be crossed over to receive HCQ at the time of unblinding.

Sub-Study 3: If the participant at any time has worsening symptoms consistent with new onset of COVID-19 disease a COVID-19 PCR test is performed. Antibody tests alone will not be used to make decisions for this study. If the PCR test is positive for SARS-CoV-2 an appropriately delegated and credentialed study team member will contact IDS and the pharmacist will indicate which arm the participant was assigned. If the participant was assigned to placebo and wishes to cross over to HCQ, IDS will provide HCQ at the same dose as the Sub-Study 3 HCQ arm and IDS will ship the HCQ to the participant. If the participant was assigned to HCQ then the participant will be advised to seek the advice of their personal physician or go to the emergency room if symptoms are becoming more worrisome.

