Duration administration	of	Sub-Study 1 at home quarantine Arm 1: HCQ 2 weeks 400 mg bid; Arm 2: Placebo 2 pills bid for 2 weeks; crossover allowed upon disease progression or lack of clearance of virus Sub-Study 3 Healthcare worker prophylaxis. Arm 1: HCQ 600 mg qd for 2 months versus Arm 2: Placebo 3 pills qd for 2 months; crossover from placebo to HCQ is allowed upon disease progression/ virus confirmation
Study design		1:1 randomization in each cohort between the arms 1 and 2
Duration of trial		Approximately 1 year

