3. Live attenuated vaccines during the study
4. Herbal and natural remedies must be avoided

7.4 Duration of Protocol Treatment and Follow-up.

Sub-Study 1 duration of treatment is up to 2 weeks or at the time of release from quarantine. HCQ will be stopped in all patients at the time of release from quarantine

Sub-Study 3 duration of treatment is 2 months with assay to assess SARS CoV2 every 2 weeks.

7.5 Crossover from Control to HCQ arm. For Sub-Study 1 all participants are un-blinded upon symptom progression (see response assessment below) after at least 7 days of treatment or upon hospitalization if this occurs prior to 7 days of treatment. If the participant was assigned to placebo, he/she has the option to crossover to receive HCQ 400 mg po bid for up to 2 weeks or until criteria for release from quarantine are met (See 1.0 primary endpoint). During these 2 weeks of HCQ treatment, the patient will continue to complete the daily diary. An appropriately delegated study team member will call the patient daily to assess worsening symptoms and AEs. Patients who are not improving will be sent to the hospital for further care. Participants who have progressive symptoms and are subsequently hospitalized as related to COVID-19 will not be crossed over to receive HCQ at the time of unblinding.

In sub-study 3 participants who have worsening symptoms as defined as fever, significantly worsening cough, shortness of breath or hypoxia but do not require hospitalization and tests positive for SARS-CoV2 virus are allowed to cross over to receive HCQ, or treated with an alternative therapy per physician's choice. Once the positive test returns, the CRC will email IDS to initiate unblinding IDS will inform the CRC and clinical investigator if the patient was on placebo. The clinical investigator will contact the subject and inform them that if they were on placebo they would have the option of being treated with HCQ 600 mg qd. If the patient agrees, the clinical investigator will place the order in EPIC for HCQ 600 mg qd through IDS. Drug will be delivered to the patient's home. During these 2 weeks of HCQ 600 mg po qd treatment, clinical investigators will call the patient every 1-3 days depending on the severity of symptoms to assess worsening symptoms and AEs. Patients who are not improving will be sent to the hospital for further care.

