Anterior nares specimen: Participants will self-collect these samples on day 0 (start date for HCQ) before the HCQ is taken, Day 3, and day 7

The PATCH Trial

Foam swab provided: Puritan 6" Sterile Standard Foam Swab w/ Polystyrene Handle (SKU # 25-1506 1PF)

Collection instructions: Use a single foam swab for collecting specimens from both nares. Insert foam swab into 1 nostril straight back (not upwards). Once the swab is in place, rotate it in a circular motion 2 times and keep it in place for 15 seconds. Repeat this step for the second nostril using the same swab. Remove foam swab and insert the swab into the supplied tube.

Storage instructions: The collected swab should be placed into the bag marked "Nares swabs collected" and the date and time of the swab collection should be filled out Redcap. The "Collected" bag is then placed in the freezer in the same sealed container as the oral fluid.

Specimen stability for all specimen types for all tests is now as follows:

Room temperature: 5 days

Refrigerated (2 °C–8 °C): 5 days

Frozen (-20 °C): 7 days

Frozen (-70 °C): Acceptable

Specimen pickup: At the end of quarantine, or end of study procedures, the nares swabs will be collected. And shipped to Quest Diagnostics to assess viral titers. Cold packs or dry ice should be used during collection and cold packs should be used during shipping to Quest.

Pill diary: When the participant is released from quarantine the electronic pill diary must be submitted electronically.

Monitoring co-inhabitants: Appropriately delegated and credentialed study team members (as example: Clinical Research Coordinator) will ask the participant about the status of co-inhabitants daily to 14 days after the quarantine is completed to determine if the participant's co-inhabitants did or did not have symptoms or tested positive for COVID-19.

8.4.2 Sub-Study 3:

SARS-CoV-2 testing: Hospital workers will be tested for SARS-CoV-2 virus by RT-PCR every month. This will be a nasopharyngeal swab that will be processed by Quest diagnostics performed during enrollment at one month and two months. This screening NP swab will provide results in EPIC for clinical action within 72 hours. Eligibility criteria to start study medication does not require a negative PCR result to return.

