10.3 Off treatment/Off Study

Each participant has the right to withdraw from the study at any time without prejudice. The investigator may discontinue any person's participation for any reason, including adverse event or failure to comply with the protocol. Should a participant withdraw from the study, the reason(s) must be stated on the case report form, and a final evaluation of the participant should be performed. Reasons for withdrawal include the following:

Progression of Disease: Remove participant from protocol therapy at the time progressive disease is documented. Progression of disease is left to the discretion of the treating physician/ sub-Investigator; however, the following guidelines are provided to help decision making for discontinuing study drug:

Sub-study 1: Progression of disease can be confirmed if there is increase in COVID-19 symptom score for 2 days in a row and is three points higher than baseline. Once criteria for release from quarantine is met in SS1 the patient is off study. Once the person is hospitalized for COVID-19 in sub-study 1 the subject is off study. Participants who have progressive symptoms and are subsequently hospitalized as related to COVID-19 will not be crossed over to receive HCQ at the time of unblinding.

Sub-study 3: Development of new symptomology consistent with COVID-19: e.g. fever, cough, shortness of breath and SARS-COV2 test positivity would lead to unblinding. If on placebo the subject can crossover to HCQ for treatment and stay on study for 14 days or release from quarantine. If the subject was on HCQ the subject is off study and will be instructed to seek medical attention through their primary care physician

Extraordinary Medical Circumstance: If at any time the treating physician feels constraints of this protocol are detrimental to the participant's health remove the participant from protocol therapy.

Participant's refusal to continue treatment: In this event, document the reason(s) for withdrawal.

Failure to comply with protocol (as judged by the investigator such as compliance below 80%, failure to maintain appointments, etc.).

Withdrawal from treatment per patient choice: Patients may withdraw from study treatment at any point in the study for any reason. These subjects are allowed to withdraw from treatment but continue to participate with any of the other study procedures for the intended 2 month period.

Delay in treatment > 7 days due to toxicity

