Given the median duration of viremia is 14-20 days in mild cases, we will assume the null hypothesis that in the placebo cohort the median time to release from quarantine is 10 days from receiving a positive test. In order for HCQ to be considered more effective in this treatment setting we aim to see a median time to release from quarantine of 5 days. These values correspond to daily hazard rates of 0.069 and 0.139 respectively. We will randomize 1:1 HCQ to control and with 100 patients with 50 in the placebo arm and 50 in the HCQ arm. The one-sided z- test (alpha=.05) will have an overall 95% power to detect a significant difference between the two groups with medians of 10 and 5 days.

Based on the new CDC guidelines for quarantine release we will modify the analysis as follows: Given the median duration of viremia is 14-28 days in mild cases, we will assume the null hypothesis that in the placebo cohort the median time to release from quarantine is 14 days from receiving a positive test. In order for HCQ to be considered more effective in this treatment setting we aim to see a median time to release from quarantine of 7 days. These values correspond to daily hazard rates of 0.048 and 0.094 respectively. We will randomize 1:1 HCQ to control and with 100 patients with 50 in the placebo arm and 50 in the HCQ arm. The one-sided z- test (alpha=.05) will have an overall 93% power to detect a significant difference between the two groups with medians of 14 and 7 days.

The *hypothesis* will be tested using a one-sided test, with a z-score corresponds to the log of the hazard-ratio for recovery between the two groups. We will obtain estimates of the hazard ratio and group median survival, and 95% CI, from Cox regression. As a secondary analysis, we will stratify the analysis, and obtain separate estimates of the hazard-ratio by group. However, we are not powered to test the interaction for significance, and we do not expect significance within group.

Given that 20 subjects were recruited and treated under the old CDC guidance, we will conduct a primary analysis based on the updated 10-days from onset criterion. For the subjects who were released under the old criterion, this number will be constructed by assessing when a patient would have been released under the new rules. We will follow that with additional secondary analyses to assess the sensitivity of the results to the change in

The PATCH Trial

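### Sub-Study 1: handling at progression differs by arm before the primary event, follow-up of HCQ progressors can be read two ways, and the Cox analysis and 93% power ignore switching

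*Protocol*

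**What the plan says.** The primary outcome of SS1 is time to release from quarantine. Progression can come first, and what follows depends on the arm.

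- **Placebo arm.** Under Protocol sections 5.0 and 7.5, a progressing placebo participant has the option of HCQ for up to two weeks or until release. Section 7.5 adds: "During these 2 weeks of HCQ treatment, the patient will continue to complete the daily diary". It also has the study team telephone daily. Participants hospitalised for COVID-19 are not crossed over.
- **HCQ arm.** Section 5.0 says: "If the patient was on HCQ then HCQ will be stopped and the patient will be asked to seek the advice" of their own doctor, or to go to the emergency room if symptoms worsen. Neither 5.0 nor 7.5 states any assessment after the drug stops.
- **Trigger.** Section 7.5 says "all participants are un-blinded upon symptom progression (see response assessment below) after at least 7 days of treatment", or earlier on hospitalisation. Section 10.3 says "Progression of disease can be confirmed if there is increase in COVID-19 symptom score for 2 days in a row" and the score is three points above baseline; like 5.0, it gives no minimum time. The Study Summary (Duration of administration) has "crossover allowed upon disease progression or lack of clearance of virus".
- **Power.** Section 13.1: "The one-sided z- test (alpha=.05) will have an overall 93% power to detect a significant difference" between medians of 14 and 7 days, with 50 per arm. The test is a one-sided z on the log hazard ratio from Cox regression. Neither 10.1 nor 13.1 mentions crossover, stopping or censoring.

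The SAP covers Sub-Study 3 only.

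**The concern.** Rescue that comes before the primary event and depends on the arm affects the comparison, and the way it does so depends on whether the stopped HCQ participant is still assessed for release.

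If every participant is followed, placebo release times include time on HCQ, and HCQ release times include time off drug. The estimated effect shrinks if HCQ works. If the HCQ progressor leaves observation when the drug stops while the placebo progressor is called daily, participants are lost from one arm only, for a reason related to outcome. If progressors are slow to recover, the remaining comparison favours HCQ even when the drug does nothing.

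The text does not choose between these, so different staff could apply different rules. According to the introduction to the protocol supplement, SS1 is still enrolling.

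**Working it through.** **Step 1. Passages on follow-up after HCQ is stopped**

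| Suggests assessment ends | Suggests assessment continues |
|---|---|
| Section 10.3 lists progression among the reasons for withdrawal. | Section 10.3 removes a progressor from protocol therapy. The SS1 off-study events it names are release and COVID-19 hospitalisation. |
| Table 4 marks the symptom score only in the treatment column. | Table 4 also marks temperature on the day of release. |
| The only clause in 10.3 that keeps participants in study procedures covers withdrawal by patient choice, over a two-month period. | Section 8.4.1 describes daily symptom calls and twice-daily temperatures with no limit by arm or drug. |
| Sections 5.0 and 7.5 state continued contact only for placebo crossovers. | Section 8.4.1 has daily contact about co-inhabitants until 14 days after quarantine. |

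Both readings are available. Co-inhabitant contact alone would not supply temperatures or symptom scores, which determine release.

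**Step 2. Reproducing the 93%**

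Inputs from section 13.1: medians 14 and 7 days (hazard ratio 2), 50 per arm, one-sided 0.05, efficacy boundaries 2.7370, 2.2814 and 1.6808 at times 24, 37.8 and 60. The printed hazards, 0.048 and 0.094, are slightly below ln 2/14 = 0.0495 and ln 2/7 = 0.0990.

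Accrual is not stated. Uniform accrual over 45 days within 60 was inferred, because it returns the printed maximum information (2000.1) and fractions (0.366, 0.674) for the 10 v 5 day design. For 14 v 7 days it gives about 88 expected events.

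Power ≈ Φ(ln HR × √(d/4) − z) = Φ(0.693 × √22 − 1.681) = Φ(1.570) = 94.2%.

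With all three boundaries, power is 94.2% on the log hazard ratio scale and 91.4% on the hazard-difference scale. The 93% therefore reproduces, with no switching in it.

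**Step 3. Everyone followed, switching at day 7**

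The switching rate q is an assumption: the share of those unreleased at day 7 who switch. Results are from 6,000 simulated trials per scenario, with the accrual and boundaries of step 2.

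| q | Two-way (placebo to HCQ hazard, HCQ to placebo hazard) | Placebo crossover only | Placebo crossover only, half the HCQ effect |
|---|---|---|---|
| 0 | 94% | 94% | 94% |
| 5% | 92% | 93% | 93% |
| 10% | 88% | 92% | 93% |
| 20% | 80% | 89% | 91% |
| 30% | 69% | 85% | 90% |

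At day 7 the expected share unreleased is exp(−0.0495 × 7) = 71% on placebo and 50% on HCQ, about 60% overall. So q = 10, 20 and 30% correspond to about 6, 12 and 18% of all randomised.

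**Step 4. No drug effect, only HCQ progressors lost**

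- Same set-up, progressors releasing at half the hazard after day 7: one-sided error 7.7, 10 and 12% at q = 10, 20 and 30%. A repeat run gave about 6–10%. With equal follow-up it was 5–6%.
- Separate model: 10, 20 or 30% of all randomised progress between days 3 and 10; follow-up is cut at day 28 and tested at 1.6808. Weibull times (shape 2) with a 14-day residual median give 8, 12 and 19%. With a 21-day residual median, runs spanned 13–45%. Exponential times give 2–8%, falling below 5% when progressors recover quickly. Equal follow-up gives about 5%.

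This reading does not cost power. With HCQ 14 v 7 effective, HCQ progressors lost and progressors releasing at half the hazard, power stays at 92–94%.

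**The case against.** The strongest reply is that section 5.0 should not be read alone. Section 8.4.1 describes daily calls for SS1 participants in general, and 10.3 names only release and hospitalisation as SS1 off-study events, whereas its Sub-Study 3 paragraph does put an HCQ progressor off study. That stands. A reader might infer that the protocol prescribes unequal follow-up by arm, but the documents do not support this. The asymmetry is explicit only in 5.0 and 7.5, and the defect is an unresolved ambiguity.

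A reader might also infer that SS1 lacks its 93% power. That is not shown. The figure reproduces, no progression rate is given, and crossover is optional and closed to hospitalised progressors. A harsher simulation gives 80, 61 and 34% power for 10, 20 and 30% of all randomised progressing. It is near a worst case: no designated progressor can be released first, stopping HCQ restores the placebo hazard at once although section 4.1.1 notes a half-life of many days, and progression is equally common in both arms.

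On the trigger, silence on timing in 5.0 and 10.3 beside a specific rule in 7.5 is not strictly a contradiction. The virus-clearance condition in the Study Summary is a genuine mismatch. It also could not be applied from the study's own swabs in time, since 8.4.1 says "At the end of quarantine, or end of study procedures, the nares swabs will be collected" and only then shipped for testing.

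Finally, dilution in an as-randomised analysis is an accepted cost of offering rescue, and a separate SS1 analysis plan may exist that is not among these documents. Both points are fair. Neither removes the need for the protocol to say how progressors are followed and analysed.

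**Conclusion.** The point holds as a should-fix. Handling at progression depends on the arm and precedes the primary event, follow-up of HCQ progressors is open to two readings, and neither the Cox analysis nor the power statement deals with switching.

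The two consequences are alternatives and should not be added together. With full follow-up the 93% is conditional on no switching; the loss is small at about 5% switching, and at 10–30% power is 88–69% (two-way) or 92–85% (placebo only). With loss of HCQ progressors only, one-sided error is about 6–12% under half-rate recovery and 2–19% in the other models with residual medians up to 14 days, and higher if recovery is slower. Size and even direction depend on how slowly progressors recover. All of these figures rest on assumed progression rates and the inferred accrual pattern.

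**What to change.** Leave the rescue itself unchanged.

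1. In section 10.3 and Table 4, state that every SS1 participant who progresses, is unblinded or stops drug keeps the same daily temperature, symptom score and call until release or a common last day, in both arms, and is analysed in the randomised arm. State in 13.1 how the Cox analysis treats crossover, stopping and hospitalisation.
2. Optionally, add a supporting analysis in which participants unblinded for progression stay in the risk set as not released until the common last day. In simulation it held about 5% error. Its power advantage (92–94% against 68–88% for the switched comparison) was obtained assuming that HCQ halves progression.
3. State that the 93% assumes no switching, and give power over a range of switching rates.
4. Reconcile the unblinding and crossover wording in the Study Summary and sections 5.0, 7.5 and 10.3. Which rule applies is for the investigators to decide.

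The cost is protocol wording, at most one extra survival analysis, continued calls to the HCQ participants who progress using the existing call system, and a power figure that becomes conditional.
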